### **I) Incidence of radiographic progression of the van der Heijde modified total Sharp score over time**

Note that missing modified total Sharp scores are imputed by the linear extrapolation method. And then a change from the baseline in the modified total SHARP score will be calculated. A change from the baseline in the modified total SHARP scores of  $\leq 0$  is considered as no progression.

## **J) Change from baseline in HAQ-DI**

The HAQ-DI is composed of 8 categories as follows: dressing and grooming, arising, eating, walking, hygiene, reach, grip and activities, for which there are at least 2 questions by category. The patient will be asked to score how difficult he/she feels it is to perform such activities using a 0 to 3 scoring (0=without any difficulty, 1=with some difficulty, 2=with much difficulty and 3=unable to do). If the patient is using assistance for any of these activities, scoring may be adjusted. For each category, the highest score given for one of the question is attributed to the category. The total score is the sum of all categories' scores divided by the number of answered categories (at least 3 categories should be answered).

### **2.1.5 Pharmacokinetic and immunogenicity variables**

Immunogenicity (anti-sarilumab antibody) and pharmacokinetic blood samples (trough concentrations) will be collected according to the study flow chart. Pharmacokinetic samples will also be collected at or near the onset and completion of the occurrence of a serious adverse event. Note that there are some missing data after Week 48 since pharmacokinetic evaluation were added after Week 48 per Protocol Amendment 8 and by that time some patients already reach more than 48 weeks of treatment.

At each sample time the result of the ADA assay will be categorized as either positive or negative, and in the case of a positive result will be further characterized as either neutralizing or non-neutralizing.

### **2.1.6 Pharmacodynamic/genomics endpoints**

Serum concentrations of IL-6 will be assessed according to the study flow chart.

### **2.1.7 Quality-of-life endpoints**

#### ***SF-36 V2 (for patients from EFC11072, ACT11575 and EFC10832 only)***

The SF-36 version 2 is a multi-purpose, short-form health survey with 36 questions. It yields scores for 8 domains (Physical Functioning, Role-Physical, Bodily pain, General health, Vitality, Social Functioning, Role-Emotional, and Mental Health, each scale is scored from 0 to 100 where higher scores indicate better health and well-being), as well as 2 summary measures of physical and mental health: the Physical Component Summary and Mental Component Summary (1).

The scoring process is summarized below:

1. Enter item response data
2. Recode item response values
3. Determine health domain scale raw scores.
4. Transform health domain scale raw scores to 0-100 scores.

5. Transform health domain scale 0-100 to norm-based scores
6. Score physical and mental component summary measures

The following table shows the construction and summary measures of the SF-36 scales:

**Table 4 - SF-36 V2 measurement model**

Summary measures	Scales	Items
Physical Component	Physical Functioning (PF)	3a, 3b, 3c, 3d, 3e, 3f, 3g, 3h, 3i, 3j
Summary (PCS)*	Role-Physical (RP)	4a, 4b, 4c, 4d
	Bodily Pain (BP)	7, 8
	General Health (GH)	1, 11a, 11b, 11c, 11d
Mental Component	Vitality (VT)	9a, 9e, 9g, 9i
Summary (MCS)*	Social Functioning (SF)	6, 10
	Role-Emotional (RE)	5a, 5b, 5c
	Mental Health (MH)	9b, 9c, 9d, 9f, 9h

MCS and PCS derived from the eight scales

The score of each of the 36 items is collected in CRF. [Appendix I](#) provides the SAS code to calculate the 8 scales, the 2 summary measure scores and standardized summary scores.

The PCS and MCS summary measure scores will be computed if at least 50% of the component scales are available. The scale scores will be computed if at least 50% of items are available within the corresponding scale. The missing items will be imputed by the mean of available items.

Change from baseline in SF-36 scores (physical component summary score and mental component summary score as well as the eight domains) will be analyzed.

## 2.1.8 Health economic endpoints

### *WPAI (for patients from EFC11072 and ACT11575 only)*

Work Productivity and Activity Impairment (WPAI) will be assessed. WPAI outcomes are expressed as impairment percentages, with higher numbers indicating greater impairment and less productivity, ie., worse outcomes, as follows:

- Q1 = currently employed
- Q2 = hours missed due to specified problem (RA)
- Q3 = hours missed other reasons
- Q4 = hours actually worked
- Q5 = degree problem affected productivity while working
- Q6 = degree problem affected regular activities Scores

Scores will be expressed in percentages.

- Percent work time missed due to problem (RA):  $100*Q2/(Q2+Q4)$
- Percent impairment while working due to problem:  $10*Q5$
- Percent activity impairment due to problem:  $10*Q6$
- Percent overall work impairment due to problem (RA):  
 $100*Q2/(Q2+Q4)+100*[(1-Q2/(Q2+Q4))*(Q5/10)]$

When deriving the 4 WPAI scores, missing data will be handled using the following rules.

- Percent work time missed due to problem (RA): The score will be missing if either Q2 or Q4 is missing.
- Percent impairment while working due to problem: The score will be missing if Q5 is missing.
- Percent activity impairment due to problems: The score will be missing if Q6 is missing.  
Percent overall work impairment due to problem (RA): The score will be missing if either percent work time missed due to problem (RA) is missing or percent impairment while working due to problem is missing.

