#### **9.1.2.7 Health economic assessment and Patient reported outcomes (PROs)**

- Health economic assessments and PROs will be performed up to Week 264 as defined in the initial study and as specified in the study flowchart (See section 1.2).

- The Functional Assessment of Chronic Illness Therapy Fatigue scale (FACIT-Fatigue) will be used to assess fatigue. The FACIT-Fatigue is a 13-item questionnaire rated 0 to 4 originally developed to measure fatigue in patients with cancer and widely used in rheumatoid arthritis patients that demonstrates good consistency and sensitivity to change. The patient will be asked to answer 13 questions rated 0 to 4 (0 = not at all, 1 = a little bit, 2 = some what, 3 = quite a bit, 4 = very much) (see [Appendix F](#)). The patient will be asked to fill in the questionnaire at different site visits (see flow chart, [Section 1.2](#))
- The Work Productivity and Activities Impairment (WPAI) will be assessed for patients coming from EFC11072 and ACT11575 only. The WPAI was developed by Margaret Reilly for assessing productivity losses by measuring the effect of general health and symptom severity on work as well as usual activity productivity. Specific-disease WPAI exists and can be adapted to different pathologies. The RA WPAI ([Appendix G](#)): instrument consists of 6 questions that ask the subject the number of hours missed from work (ie, absenteeism) due to RA, the number of hours missed from work for anything other than RA, the number of hours totally worked, as well as how much the RA does affect the productivity at work or the ability to do daily activities over the past 7 days. The instrument can be self-, interview-, or telephone-administered and takes less than 5 minutes to complete (~3 minutes). The 4 scores of the questionnaire are expressed as impairment percentages with higher numbers reflecting greater impairment and decreased productivity. The 4 scores are:
  1. Percent work time missed due to RA
  2. Percent impairment while working due to RA
  3. Percent overall work impairment due to RA
  4. Percent activity impairment due to RA

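### SAP 2.1.8: if Q5 is left blank, the WPAI missing-data rule drops an overall work impairment score that the SAP's own formula fixes at 100

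*SAP*

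**What the plan says.** The protocol (9.1.2.7) lists four WPAI scores, the third being "Percent overall work impairment due to RA". It describes the items as asking about hours missed, hours worked and "how much the RA does affect the productivity at work or the ability to do daily activities over the past 7 days". WPAI is collected only in patients from EFC11072 and ACT11575.

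SAP 2.1.8 defines the items, among them "Q4 = hours actually worked" and "Q5 = degree problem affected productivity while working", with Q2 the hours missed because of RA. It then gives the overall score as a formula in Q2, Q4 and Q5 and adds missing-data rules:

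- Percent work time missed: "The score will be missing if either Q2 or Q4 is missing".
- Percent impairment while working: missing if Q5 is missing.
- Overall work impairment: missing if "either percent work time missed due to problem (RA) is missing or percent impairment while working due to problem is missing".

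The visible text makes no exception for a patient with Q4=0. SAP Appendix C allows no imputation for the four WPAI scores, and the general rules in SAP section 2 call for observed-case analysis. Protocol 13.5.7 summarises raw value and change from baseline at each visit. Baseline is that of the parent study (protocol 13.2.1).

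**The concern.** The overall score combines time lost with reduced productivity during the time worked. When no time was worked, the second part carries no weight, so Q5 cannot affect the result. The rule nevertheless treats Q5 as essential. A patient off work for the whole recall week because of RA has nothing to report about productivity while working and may well leave Q5 blank. That patient then leaves the summary of overall impairment, although the score is known and is the worst possible.

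Two things are at stake. Mean impairment at a visit may look better than it is. And percent work time missed, which needs only Q2 and Q4, keeps the same patient at 100, so two work scores at one visit would rest on different patients for a reason the SAP does not mention.

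**Working it through.** The documents state no WPAI result to reproduce. The check is a direct evaluation of the SAP 2.1.8 formula, with and without the missing-data rule.

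**Formula.** Let a = Q2/(Q2+Q4). Then overall = 100a + 100(1−a)(Q5/10).

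**1. No hours worked.** With Q2>0 and Q4=0, a = 1. For Q2=40, overall = 100 + 100×0×(Q5/10) = 100. The result is the same for every Q2 from 1 to 80 and every Q5 from 0 to 10.

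**2. The rule applied to that case.**

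| Q2 | Q4 | Q5 | Percent work time missed | Overall under the SAP rule | Overall by formula |
|---|---|---|---|---|---|
| 40 | 0 | 10 | 100 | 100 | 100 |
| 40 | 0 | blank | 100 | missing | 100 |

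**3. Some hours worked.** With Q2=20 and Q4=20, a = 0.5 and overall = 50 + 50×(Q5/10), which runs from 50 (Q5=0) to 100 (Q5=10). Here Q5 is needed and the missing rule is justified. It is unnecessary only when Q4=0 and Q2>0.

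**4. Effect on a visit mean.** Among employed patients whose overall score is determined by their answers, let f be the share with Q4=0, Q2>0 and blank Q5, and m the mean of the others.

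- Mean with these patients kept: 100f + (1−f)m.
- Mean under the rule: m.
- Difference: f×(100−m), which is never negative.

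The documents give neither f nor m. The values below are assumptions:

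| f | m=20 | m=30 | m=40 | m=50 |
|---|---|---|---|---|
| 0 | 0 | 0 | 0 | 0 |
| 1% | 0.8 | 0.7 | 0.6 | 0.5 |
| 5% | 4.0 | 3.5 | 3.0 | 2.5 |
| 10% | 8.0 | 7.0 | 6.0 | 5.0 |

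For example, f=5% and m=40 gives 0.05×100 + 0.95×40 = 43.0 against a reported 40.0.

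**5. Effect on change from baseline.** A score lost at either end removes the patient's change.

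- Fully absent at baseline only: the lost change is (later score − 100), which is zero or negative. With an assumed later score of 25 it is −75, an improvement not counted.
- Fully absent at the visit only: the lost change is (100 − baseline), which is zero or positive. With an assumed baseline of 45 it is +55, a deterioration not counted.
- Fully absent at both: the lost change is 0.

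The net direction therefore cannot be stated in advance.

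**The case against.** The strongest objection is that the loss depends on Q5 being blank, and nothing visible says it will be. The questionnaire (protocol Appendix G) and the WPAI scoring page (SAP Appendix G) did not survive in the text. A skip instruction or a zero-hours scoring rule would be found there, and its absence from the text is not evidence that the plan lacks one. A fully absent patient who marks any value for Q5 keeps the 100. This stands, and the point is conditional for that reason. The inference that Q5 may be blank rests only on its definition and the 7-day recall period.

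A reader might also infer that the rule removes exactly the patients at the worst value of the scale. It does not. Any patient with Q5=10 scores 100 whatever the hours (step 3), and those patients are kept. The same rule also drops patients with Q4>0 and blank Q5 at any level of impairment.

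It can further be said that full absence is not hidden. Percent work time missed still shows it, SAP 2.5.3 presents the number of patients with missing data when relevant, and the WPAI scores rest on different items, so their denominators can differ anyway. This reduces the consequence, but does not justify discarding a score that the observed answers determine. For ACR response, SAP 2.5.2 already determines the result from available data where it can.

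Finally, no test or safety conclusion depends on this score. That is correct and sets the grade.

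**Conclusion.** The point holds as a conditional, minor one. As written in SAP 2.1.8, the rule discards an overall work impairment score of 100 for an employed patient with Q2>0, Q4=0 and a blank Q5, although Q2 and Q4 fix the score. At any one visit this can only lower the reported mean, or leave it unchanged if all other scores are also 100. For change from baseline the direction depends on timing.

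The size is f×(100−m). It is zero if fully absent patients answer Q5, or if there are none, and 0.5 to 8.0 points over the assumed ranges f=1–10% and m=20–50. A reader might take such figures as an estimate of bias in this trial. The documents do not support that, because they give neither input nor the completion pattern of Q5.

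The reach is limited to one of four WPAI scores, summarised descriptively, in employed patients among the 1283 + 7 = 1290 who rolled over from EFC11072 and ACT11575. The primary safety endpoint is not affected.

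**What to change.** In SAP 2.1.8 and in the WPAI row of Appendix C, state that if Q1=yes, Q2>0 and Q4=0, overall work impairment is 100 whether or not Q5 is answered, and that the missing rule for Q5 applies to this score only when Q4>0. This is not imputation, since it returns the value of the SAP's own formula and changes nothing for a patient who did answer Q5. If SAP Appendix G already contains such a rule, a cross-reference from 2.1.8 is enough.

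Derive the parent-study baseline scores by the same rule, so that change from baseline uses one definition. The re-derived baselines may then differ from values already reported for the parent studies, which deserves a footnote.

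The same edit should say what happens when an employed patient has Q2=0 and Q4=0, where the formula is 0/0 and the visible text gives no rule.

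The cost is one or two sentences and a line of code, plus re-derivation of the parent-study baselines. The items are already collected.

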### ***FACIT-Fatigue (for patients from EFC11072, ACT11575 and EFC10832 only)***

The Functional Assessment of Chronic Illness Therapy Fatigue scale (FACIT-Fatigue) will be used to assess fatigue. The FACIT-Fatigue is a 13-item questionnaire rated 0 to 4 originally developed to measure fatigue in patients with cancer and is widely used in RA patients to demonstrate good consistency and sensitivity to change. The patient will be asked to answer 13 questions rated 0 to 4 (0=not at all, 1=a little bit, 2=some what, 3=quite a bit, 4=very much). The fatigue scale has 13 items, with 52 as the highest possible score. A higher score in the fatigue scale corresponds to a lower level of fatigue and indicates better Quality of Life.

To calculate the FACIT-fatigue score, the response scores on negatively phrased questions are reversed and then the 13 item responses are added. Eleven items with responses have their scores reversed (item score = 4 – response, if the response is not missing), and two items (items 7-8) have their responses unchanged ([Appendix F](#)). All items are added so that higher scores correspond to less fatigue. In cases where individual questions are skipped, scores are prorated using the average of other answers in the scale.

$$FACIT-Fatigue = 13*[sum(reversed items)+sum(items 7-8)]/number\ of\ answered\ items$$

### ***Sleep questionnaire (for patients from EFC11072 and ACT11575 only)***

RA like other chronic illness is associated with sleep disturbances. Sleep disturbances is linked to pain, mood and disease activity. The effect of sarilumab on pain will be assessed on a sleep questionnaire VAS scale ranges from 0 (sleep is not a problem) to 100 (sleep is a major problem).

### ***WPS-RA (for patients from EFC10832 only)***

The rheumatoid arthritis-work productivity survey (WPS-RA) is a validated questionnaire that evaluates productivity limitations within work and within home associated with RA over the previous month. The questionnaire is interviewer-administered and is based on patient self-report.

It contains 9 questions addressing employment status (1 item), productivity at work (3 items) and within and outside the home (5 items) ([Appendix H](#)).

## **2.2 DISPOSITION OF PATIENTS**

This section describes patient disposition for both patient study status and the patient analysis populations for LTS11210 only, unless otherwise specified.

- All screened patients are defined as those patients who signed the informed consent.
- All enrolled patients are defined as all patients with signed informed consent who met the eligibility criteria to enter into LTS11210.
- The Safety population consists of all enrolled patients who received at least one dose of the LTS11210 study medication.

For patient study status, the total number of patients for each one of the following categories will be presented using a summary table:

- All screened patients (informed consent signed)
- Screen failure patients and reasons for screen failure (not eligible per eligible CRF page)
- Non-enrolled but treated patients
- All enrolled patients by previous studies
- Enrolled but not treated patients
- Enrolled and treated patients
- Patients who had dose reductions
- Patients who discontinued study treatment by main reason for permanent treatment discontinuation
- Status at last study contact

For all categories of patients (except for the screened and non-enrolled categories), percentages will be calculated using the total of all enrolled patients as the denominator. Reasons and time to treatment discontinuation will be supplied in tables giving numbers and percentages. This summary will be further sub-grouped by region and by prior biological use.

A patient is considered as lost to follow-up at the end of the study if he/she is not assessed at the last protocol planned visit.

All major or critical deviations potentially impacting analyses, drug dispensing irregularities and other major or critical deviations will be summarized in tables giving numbers and percentages of deviations.

The analysis populations for safety, efficacy and PK will be summarized in a table by patient counts on the enrolled patients.

- Safety population (for safety and efficacy analyses),
- PK population.

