### **12.1.2.2 Visit 1/Visit 2: Patients enrolling From EFC10832, SFY13370, EFC13752 and EFC11072 Part B Cohort 2**

**The following assessments will be completed at Visit1/Visit 2 by patients enrolling in the LTS11210 study from EFC10832, SFY13370, EFC13752 or EFC11072 Part B Cohort 2.**

A specific written informed consent form (WICF) should be signed and dated to enter the LTS11210 prior to any assessment.

The patient will be proposed to enter this study if eligible. If not eligible or unwilling to enter this long term study then he or she will have a follow-up visit 6 weeks after the completion of the study EFC11072, SFY13370, EFC10832, or EFC13752.

**The following V1/V2 assessments and lab procedures for this study will be obtained from the End of Treatment visit in the study EFC11072, SFY13370, EFC10832, or EFC13752. Results of these assessments (if available) should be reviewed prior to patient's inclusion in the study as a part of eligibility assessment:**

- The Investigator or designee will enquire regarding AE/SAEs
- Physical examination
- Vital signs including body temperature, blood pressure and heart rate
- Body weight (kg).
- Clinical laboratory determinations including hematology, clinical chemistry profile, LFTs and lipids.
- Results of urinalysis (dipstick) for: specific gravity, pH, glucose, blood, ketones, proteins, bilirubin, urobilinogen, nitrate, leukocytes (to be included in eligibility assessment). If positive for proteins, results of microscopic analysis performed by central laboratory.
- Results of pregnancy test if female of child bearing potential
- 12 – lead ECG
- Tuberculosis assessments
- Completed joint examination assessing tender and swollen joints
- Completed relevant questionnaires: HAQ, patient's global assessment, patient's pain questionnaire, physician global assessment.
- Completed health economic assessment questionnaires.
- Laboratory results for acute phase reactants: hs-CRP. The investigator, patient and sponsor will be blind to the results of the hs-CRP at Visit V1/V2. The investigator is advised not to do a local CRP testing unless needed for safety reasons.
- Blood sample for PK (sarilumab), Serum IL-6 (for EFC11072 patients), and anti-sarilumab antibody.
- Serum sample for future biomarker tests (except EFC13752 patients)

- Laboratory results for rheumatoid factor (RF).
- Laboratory results for ANA (if ANA titer is >1:160 obtain Anti-ds DNA).

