### **13.3 DISPOSITION OF PATIENTS**

The total number of patients for each of the following categories will be presented in the clinical study report:

- All screened patients: all patients who have signed the informed consent
- All patients entered in the LTS: all patients who have signed the informed consent and are eligible to enter the study.
- Safety population: defined as all patients entered in the LTS who have received at least 1 dose of the study treatment in the LTS11210,
- Patients who discontinued the treatment and reasons for treatment discontinuation.

The percentage will be calculated using the total number of all patients entered in the LTS as the denominator.

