### **13.4 ANALYSIS POPULATIONS**

The primary analysis population is the safety population which is defined as all patients who have received at least 1 dose of the study treatment in the LTS11210.

All safety analyses and efficacy analyses will be performed based on the safety population.

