### **2.3.1 Safety populations**

Safety population is defined as all enrolled patients who have received at least one dose of the study treatment in LTS11210.

All analyses will be performed on the safety population based on previous treatment prior to enrollment into LTS11210. This will allow for assessment of any differences between treatment groups based on previous treatment.

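### The SAP safety population is conditional on meeting the eligibility criteria, so patients it classes as treated but not enrolled are left out of the safety summary tables

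*SAP*

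**What the plan says.** SAP 2.2 makes eligibility part of the meaning of enrolment: "All enrolled patients are defined as all patients with signed informed consent who met the eligibility criteria to enter into LTS11210". The same section builds the main analysis set on that term: "The Safety population consists of all enrolled patients who received at least one dose of the LTS11210 study medication". SAP 2.3.1 repeats it: "Safety population is defined as all enrolled patients who have received at least one dose of the study treatment in LTS11210". The disposition table in SAP 2.2 has a row for "Non-enrolled but treated patients", so the plan expects that such patients may exist.

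The protocol gives two definitions. Section 13.3 requires a treated patient to have entered the study, and describes those who entered as "all patients who have signed the informed consent and are eligible to enter the study". Section 13.4 describes the safety population as one "which is defined as all patients who have received at least 1 dose of the study treatment in the LTS11210", with no eligibility condition, and the synopsis agrees with 13.4.

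**The concern.** The primary objective is long-term safety, and SAP 2.1.3 names the incidence of adverse events as the primary endpoint. A safety population would normally be fixed by exposure to the drug. Here it is fixed by exposure plus eligibility, so a patient known to have been dosed can fall outside the tables that carry the primary endpoint.

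Several exclusion criteria in protocol 7.3 concern safety: an earlier adverse event that led to discontinuation (E03), a current abnormality (E11), a long treatment hold (E13), or a criterion for permanent discontinuation already met (E14). Patients dosed despite one of these may well be at higher risk than the rest. If so, leaving them out lowers the reported incidence and the exposure-adjusted rates. Two programmers working from different sections could also build different primary populations.

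**Working it through.** No power or error-rate calculation applies. The check compares the definitions and then follows one patient through the plan.

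**Definitions**

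| Place | Condition for the safety population |
|---|---|
| Protocol synopsis, statistical considerations | At least one dose |
| Protocol 13.3 | Consented, eligible, at least one dose |
| Protocol 13.4 | At least one dose |
| Protocol 13.5.4 (safety analyses) | Refers to 13.4 |
| SAP 2.2 and 2.3.1 | Consented, met eligibility criteria, at least one dose |

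**A dosed patient who is not enrolled**

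1. SAP 2.2: counted in one disposition row.
2. SAP 2.3: separate reporting is promised only for the opposite group, those enrolled but never treated.
3. SAP 2.4.4: all safety analyses use the safety population unless otherwise specified, so the patient is out. (The section number cited there is 2.3.2, the efficacy population, which SAP 2.3.2 equates with the safety population.)
4. SAP 2.4.4.1: percentages use the safety population as denominator, and the treatment-emergent and adjudicated cardiovascular summaries name it. The serious and special-interest event summaries fall under the general rule in 2.4.4. No exception is stated.
5. SAP 2.4.4.2: death incidence, death rates and death summaries are on the safety population.
6. SAP 2.3.3: the PK and ADA populations are subsets of the safety population, so they inherit the exclusion.
7. SAP 2.4.4.1 and 2.4.4.2: the listings of adverse events, serious events, adjudicated events and deaths are not expressly limited to the safety population, so the patient's events may appear there.

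**Study size**

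The SAP gives approximately 2000 patients.

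- SAP 1.3: 243 + 1040 + 7 + 168 + 454 + 111 = 2023.
- SAP 1.1: 1283 + 7 + 456 + 168 + 111 = 2025.

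Both agree with the stated figure. The difference of 2 comes from EFC10832 alone (456 − 454) and is not explained.

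**Illustration of size**

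The documents do not give the number *k* of treated, non-enrolled patients. Assume a base of 2023 and an event seen in 20 patients (20/2023 = 0.99%). If no restored patient had the event, incidence becomes 20/(2023 + *k*). If all had it, incidence becomes (20 + *k*)/(2023 + *k*).

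| *k* (assumed) | *k*/2023 | None had the event | All had the event |
|---|---|---|---|
| 1 | 0.05% | 0.99% | 1.04% |
| 2 | 0.10% | 0.99% | 1.09% |
| 5 | 0.25% | 0.99% | 1.23% |
| 10 | 0.49% | 0.98% | 1.48% |
| 20 | 0.99% | 0.98% | 1.96% |

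The denominator hardly moves. Any material change comes from events in the restored patients, and the last column is a worst case.

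**The case against.** **The SAP follows the protocol.** A reader might infer that the SAP departs from a single all-treated definition in the protocol. It does not: protocol 13.3 has the same eligibility condition, so the inconsistency starts inside the protocol. This stands. Even so, 13.5.4 sends safety analyses to 13.4, and SAP 2.2 and 2.3.1 do not match 13.4.

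**The excluded group may be narrower than it looks.** It is tempting to argue that anyone dosed before a failing laboratory result arrives is removed. For patients entering at the combined Visit 1/Visit 2, protocol 12.1.2.2 says: "Results of these assessments (if available) should be reviewed prior to patient's inclusion in the study as a part of eligibility assessment". The first dose is given at that same visit. But the synopsis has patients enrolled on Day 1 after eligibility is confirmed, and 12.1.2.2 puts kit allocation and dosing after that confirmation. It treats later laboratory results as a matter for on-treatment action. SAP 2.2 ties screen failure to the record made at entry: "Screen failure patients and reasons for screen failure (not eligible per eligible CRF page". A patient recorded as eligible, dosed and later found in breach may therefore remain enrolled and be summarised as a deviation. SAP 2.2.1 gives a different example of dosing outside the process, a non-screened patient who receives study drug. This stands as a plausible reading, but the SAP does not state it.

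**The events are not lost.** A reader might infer that these patients disappear from safety reporting. The documents do not support that: the listings are unrestricted, and protocol 10.3 and 10.6 require events and safety observations to be reported in the clinical study report. This limits the point to summary tables and rates.

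**The study is descriptive.** It has no control arm and no planned testing, so no inference is overturned. True, but descriptive incidence is the main result here.

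**Conclusion.** The point holds for the summary tables and rates. Read literally, SAP 2.2 and 2.3.1 and protocol 13.3 leave patients known to have received sarilumab out of the primary-endpoint summaries, while the synopsis and protocol 13.4 include them.

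The size cannot be derived. The number of affected patients is not stated and may be small or zero. The gap of 2 between the SAP 1.1 and 1.3 counts cannot be read as that number, and any assumed percentage of ineligible but dosed patients has no basis in the documents. A downward bias also rests on an assumption, that these patients have more events than the others. If they do not, the effect is negligible.

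The text should still be corrected. The rule as written omits exposed patients, the plan foresees that they may exist, and nothing in either document justifies excluding them.

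**What to change.** In SAP 2.2, SAP 2.3.1 and protocol 13.3, define the safety population as all patients who received at least one dose of sarilumab in LTS11210, regardless of eligibility or enrolment status. The words on eligibility and enrolment would be new text, but the content is consistent with protocol 13.4 and the synopsis.

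Keep the disposition row for treated, non-enrolled patients and state that they are included in all safety summaries and rates. Add a sentence that a patient recorded as eligible at dosing and later found in breach stays in the population and is reported as a deviation. Correct the cross-reference in SAP 2.4.4 from 2.3.2 to 2.3.1.

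The cost is about one sentence per section and no new assessments. The downside is that efficacy tables, which use the same population, may gain a few ineligible patients.
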